6.1. Adverse Events

The verbatim terms used in the eCRF by investigators to identify adverse events will be coded using the latest version of the Medical Dictionary for Regulatory Activities (MedDRA) at the time of database lock. Any AE occurring on or after the initial administration of ATIMP within 6 months is considered to be treatment emergent. All reported treatment-emergent adverse events will be included in the analysis. For each adverse event, the number and percentage of subjects who experience at least 1 (one) occurrence of the given event will be summarized by age group, treatment group and overall.

Summary tables will be provided for the frequency and incidence of subjects experiencing the following treatment-emergent adverse events:

- AEs
- Serious AEs (SAEs)
- AEs leading to termination of study participation
- AEs by severity
- AEs by relationship to ATIMP
- AEs by relationship to ATIMP surgery
- Death
- AEs of interest related to ocular inflammation

- Inflammation in cohorts before and after the addition of subTenons triamcinolone injection to the protocol

Summaries of adverse events by system organ class and dictionary-derived (preferred) term will also be provided.

In addition to the summary tables, accompanying listings will be provided for subjects who experience:

- AEs
- SAEs
- AEs leading to termination of study participation
- Death (if any)
- AEs of interest related to ocular inflammation.

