5.11.3.5 Notifications

5.11.3.5.1 Notifications by the Investigator to

All adverse events will be recorded in the participant's medical notes and the CRF from the date of written informed consent until last study visit.

must be notified of all SAEs and SUSARs within 24 hours of the investigator becoming aware of the event during this period. The investigator will respond to any SAE queries raised by
as soon as possible. After last visit, any SAE reported to the investigator and considered causally related to trial treatment should be reported as part of the follow up study. For any participants that do not go into the follow up study, then SAEs that occur after the end of the trial and that may be attributed to ATIMP administration should be reported to the relevant regulatory agencies.

The SAE form must be completed by the investigator (the consultant named on the delegation of responsibilities list who is responsible for the participant's care) with attention paid to the grading, and causality of the event. In the absence of the responsible investigator, the SAE form should be completed and signed by a member of the site trial team and emailed as appropriate within the timeline. The responsible investigator should check the SAE form at the earliest opportunity, make any changes

necessary, sign and then email to _____. Systems will be in place at the site to enable the investigator to check the form for clinical accuracy as soon as possible.

The minimum criteria required for reporting an SAE are the trial number and date of birth, name of reporting investigator and sufficient information on the event to confirm seriousness. Any further information regarding the event that is unavailable at the time of the first report should be sent as soon as it becomes available.

The SAE form must be scanned and sent by email to the trial team on

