The study conduct was substantially impacted by the COVID-19 pandemic. In particular, the pandemic caused delayed and missed visits to several subjects in the randomized dose expansion phase of the study. In addition, there were delays beyond the planned 6 months for treatment in the deferred treatment arm of the study. To allow greater flexibility in the management of protocol

deviations and timing of treatments in the deferred treatment arm of the study as a result of the COVID-19 pandemic, the protocol was amended in accordance with Health Authority guidance.

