1.3. Statistical Hypotheses for Trial Objectives

1.3.1. Primary Safety Hypothesis

The objective of the dose escalation phase is to estimate the proportion of subjects who experienced the primary safety outcome. No formal hypothesis testing will be conducted.

The primary safety outcome is defined as any of the events delineated below and occurring during the 9 weeks following administration, at least possibly related to the ATIMP, not the surgery alone:

- Reduction in visual acuity by 15 Early Treatment Diabetic Retinopathy Study (ETDRS) letters or more
- Severe unresponsive inflammation (defined in Section 4.2.1 of the protocol)
- Infective endophthalmitis
- Ocular malignancy
- Grade III or above non-ocular suspected unexpected serious adverse reaction (SUSAR) (Protocol MGT009, Section 5.11.3.4.2 Severity or Grading of Adverse Events).

Safety will be assessed for 12 months following ATIMP administration for immediate treatment participants in this study (Protocol MGT009) by study phases (dose escalation, dose confirmation and expansion phases) and overall, comparing with 6 months data in deferred treatment arm prior to treatment. Safety outcome captured in a separate long-term follow-up study (Protocol MGT010) for a further 4 years will be summarized separately.

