1.4. Randomization and Blinding

In dose escalation phase, up to 18 adult participants will be administered one of 3 different doses of the ATIMP in cohorts of 3 participants at a time. Based on toxicity data, the IDMC will make a recommendation on the dose to administer to the next cohort of 3 participants.

Once an acceptable safety profile has been established in adults, the IDMC will agree the maximum tolerated dose in adults, which will be confirmed in 3 pediatric participants.

In the expansion phase, up to 48 subjects were randomized to 1 of 3 arms in a 1:1:1 ratio (Immediate low dose administration: Immediate intermediate dose administration: deferred administration). Subjects randomized to the deferred administration group were further randomized to receive the low or intermediate dose in a 1:1 ratio. The eye selected for administration was also randomized at the start of the expansion cohort. All aspects of randomization occurred on completion of screening. The three treatment groups of the randomized expansion phase will be stratified by age at date of informed consent (<25 years, \geq 25 years) to balance for disease severity between treatment groups with age used as a surrogate for severity.

Visual function assessors and reading centers are masked to treatment (dose levels and immediate vs. deferred treatment). Neither study site nor sponsor personnel were masked to treatment.

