2.3.3. Safety Analysis Set

Safety analyses will be performed using the safety analysis set, which includes all immediate treatment subjects (regardless of study phase) who were administered ATIMP, and all deferred subjects who completed their last baseline assessment during the deferred period prior to treatment. Safety analyses will be performed according to actual treatment received.

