6.2. Clinical Laboratory Tests

Clinical laboratory tests will be displayed for the subjects included in the safety analysis set. Hematology, clinical chemistry, glucose, serology and polymerase chain reaction (PCR) laboratory tests will be presented.

Hematology and clinical chemistry observed values will be summarized at each assessment time point using shift table by parameter (unit). Number of subjects and percentage with values outside of normal range will be summarized through Week 52.

Individual hematology and clinical chemistry values outside of normal range will be listed by subject.

Serology data will be listed and summarized at each assessment by age group, treatment group and overall.

All PCR values will be summarized by tissue and listed.

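### The 6-month, ATIMP-anchored definition of treatment-emergent AEs drops months 7 to 12 from the AE tables and leaves no untreated comparator

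*SAP*

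**What the plan says.** SAP 6.1 defines the event set for AE analysis: "Any AE occurring on or after the initial administration of ATIMP within 6 months is considered to be treatment emergent". The tables listed under that heading (all AEs, SAEs, AEs ending participation, severity, relationship to ATIMP and to surgery, death, ocular inflammation) are described as tables of treatment-emergent events, by age group, treatment group and overall.

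SAP 1.3.1 sets a different horizon: "Safety will be assessed for 12 months following ATIMP administration for immediate treatment participants in this study". It then names the comparator: "comparing with 6 months data in deferred treatment arm prior to treatment". SAP 2.3.3 accordingly admits to the safety analysis set "all deferred subjects who completed their last baseline assessment during the deferred period prior to treatment". SAP 2.5 gives these subjects their own Study Day 1, the end of the last baseline visit, but SAP 6.1 does not use it.

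Other safety summaries run longer. For laboratory tests, SAP 6.2 says: "Number of subjects and percentage with values outside of normal range will be summarized through Week 52". SAP 6.3 does the same for vital signs. Protocol 5.11.3.5.1 has AEs entered in "the CRF from the date of written informed consent until last study visit".

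**The concern.** Safety is the primary objective. Under the definition as written, the reported incidence of AEs, SAEs, deaths and ocular inflammation would describe 6 months after dosing, although SAP 1.3.1 says 12. An SAE or death starting in month 8 has no assured place in any tabulated percentage. The primary safety outcome covers only 9 weeks, and the long-term study is summarised separately and begins, for these participants, after month 12.

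The second consequence concerns the control. The expansion phase provides a randomised untreated group for about 6 months. Its AE experience is the natural background against which to read events after surgery and ATIMP. A definition that requires ATIMP excludes every event in that period, so an untreated column would be zero by construction or absent.

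**Working it through.** The SAP gives no figure that depends on this definition, so there is none to reproduce. The check compares planned person-time with the definition.

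**Inputs**
- Participants followed for 12 months after ATIMP, at the ceilings in Protocol 5.7 and 4.3.2.2.5: 18 escalation + 5 paediatric + 32 immediate expansion = 55. SAP 1.4 refers to the adult dose "which will be confirmed in 3 pediatric participants", which gives 18 + 3 + 32 = 53.
- Deferred arm: up to 16, with 6 months planned before ATIMP and 6 months after (Protocol 4.3.1).
- Complete follow-up is assumed.

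**Step 1. Post-dose time outside the window, 12-month participants**
- 55 × 12 = 660 person-months, of which 55 × 6 = 330 fall outside (50%).
- With 3 children: 53 × 12 = 636, of which 53 × 6 = 318 fall outside (50%).

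**Step 2. Adding the deferred arm after treatment**
- 16 × 6 = 96 person-months, all inside the window as planned.
- Omitted share: 330 / (660 + 96) = 330/756 = 43.7%, or 318 / (636 + 96) = 318/732 = 43.4%.

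**Step 3. Untreated deferral time**
- 16 × 6 = 96 person-months as planned, none of which can yield a treatment-emergent event.
- SAP 1.2 reports that "there were delays beyond the planned 6 months for treatment in the deferred treatment arm of the study". The Week 26 deferral window in SAP 2.1 runs to Day 365. If every deferral lasted that long the total would be about 16 × 12 = 192, which is an upper bound and not an estimate.

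**Step 4. Chance that the tables miss someone**

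The documents give no late event rate. Assume a risk p per participant of a first event of a given type in months 7 to 12. The chance that at least one such participant is missed is 1 − (1 − p)^n.

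| Assumed p | n = 53 | n = 55 |
|---|---|---|
| 1% | 41% | 42% |
| 2% | 66% | 67% |
| 5% | 93% | 94% |

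**Step 5. Does another table supply the comparison?**

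SAP section 6 tabulates the primary safety outcome for deferred subjects before treatment. SAP 1.3.1 defines that outcome as an event in the 9 weeks after administration that is at least possibly related to ATIMP. An untreated subject cannot have one, so that column carries no background rate either.

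**The case against.** - **The tables may be wider than they look.** The SAP 6.1 sentence on system organ class and preferred term summaries does not repeat the treatment-emergent restriction, and table layouts sit in a Data Presentation Specifications document that is not available. The first part stands: the scope of that sentence is unclear, and it could cover late and pre-ATIMP events. The second does not rescue the plan, because a table shell should not override a SAP definition.
- **Late events are not lost.** The listings of AEs, SAEs and deaths carry no such restriction, and the trial has at most 71 participants. This stands for individual events. A listing still gives no planned incidence or denominator.
- **The SAP never names AE tables as the vehicle for the comparison.** True, but the primary safety outcome cannot provide it (step 5), and SAP 1.3.1 speaks of safety in general.
- **Six months may be deliberate**, to match the deferred arm's post-treatment follow-up or the Week 26 comparison. The SAP does not say so, and the ATIMP condition would still empty the control column.
- **The figures use ceilings.** This stands. SAP 1.2 describes escalation cohorts of 3 to 4. Assuming three unexpanded cohorts (9 to 12 adults) with 3 children and 32 immediate participants, n is 44 to 47. The omitted time is then 44 × 6 = 264 to 47 × 6 = 282 person-months, still half of the 12-month total, and the step 4 probabilities fall to about 36–38%, 59–61% and 90–91%. Half the person-time is also not half the events, since surgical and inflammatory risk is concentrated early.

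**Conclusion.** The concern holds. SAP 6.1 conflicts with SAP 1.3.1 and 2.3.3 on both the length of follow-up and the comparator, so this is more than missing detail. Up to 330 of 660 post-dose person-months (50%) in participants followed for 12 months are outside the listed AE tables, or 43% to 44% of all planned post-dose time when the deferred arm is included. All untreated deferral time, 96 person-months as planned, is uncountable.

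These figures assume the protocol's maximum numbers and complete follow-up. The event probabilities rest on assumed late risks, and early-onset events such as post-operative inflammation belong at the low end. The primary safety outcome, the DLE summary and the laboratory and vital-sign summaries do not depend on the definition. The supplied protocol's amendment log ends at v11.0 while the SAP cites v12.0, so the protocol's AE-recording text is supporting evidence only. The conflict rests on the SAP alone.

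**What to change.** 1. Define treatment-emergent as onset from ATIMP administration through the last study visit, and tabulate months 0–6 and 6–12 separately. If the 6-month window was meant to match the deferred arm's post-treatment follow-up, say so; the split keeps that comparison.
2. Add one table for the randomised comparison: AEs in the immediate expansion arms from Day 1 to Week 26, against AEs in the deferred arm from its Study Day 1 (SAP 2.5) to the day before ATIMP.
3. Report exposure-adjusted rates beside the counts, because COVID-19 lengthened some deferral periods.
4. State whether the system organ class and preferred term summaries and the listings cover all AEs or only treatment-emergent ones.

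The cost is SAP wording and one extra set of AE tables. The supplied protocol already has AEs recorded from consent to the last visit, so no new data are needed. Reported AE incidence will be higher than under the 6-month rule.

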6.2. Clinical Laboratory Tests

Clinical laboratory tests will be displayed for the subjects included in the safety analysis set. Hematology, clinical chemistry, glucose, serology and polymerase chain reaction (PCR) laboratory tests will be presented.

Hematology and clinical chemistry observed values will be summarized at each assessment time point using shift table by parameter (unit). Number of subjects and percentage with values outside of normal range will be summarized through Week 52.

Individual hematology and clinical chemistry values outside of normal range will be listed by subject.

Serology data will be listed and summarized at each assessment by age group, treatment group and overall.

All PCR values will be summarized by tissue and listed.

6.3. Vital Signs and Physical Examination Findings

Vital sign parameters including height, weight, pulse, blood pressure (systolic and diastolic), respiration rate, arterial oxygen saturation, temperature will be summarized at each assessment time point using shift table. Number of subjects and percentage with values outside of normal range will be summarized through Week 52.

Individual physical examination data outside of normal range will be listed by subject.

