4.1.5.6 Risk of adverse effects of corticosteroids

Candidates will be screened for contra-indications to transient immune suppression by corticosteroids. Possible adverse effects of short-term systemic corticosteroid use include increases in blood pressure and blood sugar, weight gain, changes in mood or behaviour, increased risk of infections, increased intraocular pressure and cataracts. Local steroids used on or near the eye can cause increased intraocular pressure and cataracts.

The possibility of steroid-induced adverse effects will be monitored regularly. In particular, blood pressure on day 1, day 3, day 7, week 2, week 4, week 6, and week 9, and blood glucose, renal function and liver function (at baseline and day 1, day 7, week 2, week 4, week 6 and week 9 after surgery).

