5.3.1.2 Participant Inclusion Criteria

Inclusion in the trial will be limited to individuals who meet the following criteria:

- 1. Are males aged 5 years or older
- Have X-linked retinitis pigmentosa confirmed by a retinal specialist (CI or PI)
- Have relatively symmetrical retinal disease both structurally and functionally defined as < 15
 letters [Best Corrected Visual Acuity (BCVA)] difference between eyes
- 4. Have a predicted disease-causing missense or null mutation in *RPGR* confirmed in an accredited laboratory
- 5. Evidence of relative preservation of retinal structure at the macula

- 6. Evidence of impaired navigation in dim illumination on Mobility assessment in **both** eyes monocularly; defined by either an inability to complete the visual mobility maze at the 1 lux level, or the time taken to complete the maze at either 1 or 4 lux being greater or equal to 12 seconds.
- 7. Are able to give informed consent or assent, with the guidance of their parent/guardian where appropriate: children aged 5-6 years will not be asked to provide assent
- 8. Are able to undertake age appropriate clinical assessments at the trial sites as specified in the protocol
- 9. Are willing to use barrier and spermicide form of contraception or will be sexually abstinent (when this is in line with the participant's preferred and usual lifestyle) for at least 12 months following ATIMP administration
- 10. Are willing to give consent for the use of blood and blood components collected through the trial for the investigation of immune responses to the ATIMP

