5.4.2.3 Subsequent Assessments

On the 1st postoperative day, a full clinical ocular examination will be performed. Visual acuity, intraocular pressure, the degree of postoperative intraocular inflammation and the area of any residual retinal bleb will be documented. Fundus photography, ocular examination, intraocular pressure and SD-OCT will be performed at day 1 and each subsequent visit post ATIMP administration.

A standard post-vitrectomy treatment regimen of topical antibiotic (chloramphenicol 0.5% qds for 7 days) and steroid (dexamethasone 0.1% qds for 4 weeks and then bd for a further 2 weeks) will be prescribed to minimise inflammation and protect against infection postoperatively.

Intraocular pressure of greater than 30 mmHg will be managed with systemic therapy where indicated with specialist advice sought as required.

Participants will be maintained on oral prednisolone (or other as appropriate) for 8 weeks following administration of ATIMP as described above (Section 5.4.2.2.1: Pre-operative procedure). The possible development of steroid-induced adverse effects will be monitored regularly. In particular, blood pressure will be measured, and blood glucose, renal function and liver function will be evaluated through blood biochemistry at the time points specific in Table 3, Trial Assessments (Dose Escalation Phase, Paediatric Dose Confirmation Phase, and Immediate Treatment Arms of Dose Expansion Phase) and Table 4: Trial assessments (Deferred Treatment Group)

Both safety and efficacy of the ATIMP will be evaluated at various time points up to 12 months after ATIMP delivery. Evaluations will comprise primarily ocular assessments. The nature and schedule (Section 5.6: Trial Assessments) of these is described below.

(i) Clinical assessment of intraocular inflammation

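### SAP 6.3 plans no change-from-baseline summary of weight or blood pressure, so steroid-related increases that cross no limit and are not reported as adverse events appear in no planned table

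*SAP*

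**What the plan says.** SAP 6.3 covers all vital signs in two sentences. The first names "Vital sign parameters including height, weight, pulse, blood pressure (systolic and diastolic), respiration rate" and ends "respiration rate, arterial oxygen saturation, temperature will be summarized at each assessment time point using shift table". The second adds: "Number of subjects and percentage with values outside of normal range will be summarized through Week 52". Neither sentence gives a range or says how the shift categories are formed. Neither asks for a split by age group, although SAP 6.1 does so for adverse events and SAP 6.2 for serology. The only listing in SAP 6.3 is of physical examination findings.

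Protocol 4.1.5.6 says: "Possible adverse effects of short-term systemic corticosteroid use include increases in blood pressure and blood sugar, weight gain". It goes on to say that steroid effects will be checked regularly and sets a schedule: "In particular, blood pressure on day 1, day 3, day 7, week 2, week 4, week 6, and week 9". Protocol 5.4.2.3 gives the exposure: "Participants will be maintained on oral prednisolone (or other as appropriate) for 8 weeks following administration of ATIMP". The notes to Tables 3 and 4 in Protocol 5.6 count height and weight among the vital signs. Protocol 5.3.1.2 opens eligibility to children: "Are males aged 5 years or older".

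**The concern.** A shift table reports movement between categories. It does not report how far a value moved. Where the parameter has a recognised reference range, the table can at least flag movement into an abnormal band. Absolute weight and height have no such range, so for them neither planned summary has an obvious meaning. For blood pressure in children the reference band depends on age, and the SAP text does not say which band applies.

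What is at stake is the description of two possible steroid effects that the protocol itself names. A general drift in weight or blood pressure over the 8-week course could leave every participant in the same category, and the report would contain no mean, spread or maximum from which a reader could see it. The measurements needed are already being collected.

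**Working it through.** The plan gives no figure to reproduce here. The check is of the text, followed by one illustration on assumed values.

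**Where a change in weight or blood pressure could appear**

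| Planned output | Source | Shows size of change? |
|---|---|---|
| Shift table by visit | SAP 6.3 | No, only category movement |
| Count and % outside range | SAP 6.3 | No |
| N, mean, SD, median, range for weight and height | SAP 4.1 | No, baseline only |
| Change from baseline by visit | SAP 5.3.3 | Yes, but only for primary and secondary efficacy endpoints |
| Adverse event tables and listings | SAP 6.1 | Only if the change is recorded as an event |

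Under Protocol 5.11.3.4, an abnormal test result becomes an adverse event when it is clinically significant. An increase that crosses no limit and is not so judged therefore falls through every row.

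**Which limits the documents contain.** The only blood pressure limit is the eligibility cut-off of 160/100 mmHg in Protocol 5.3.1.3. It defines uncontrolled hypertension, is not a normal range, and does not vary with age. There is none for weight or height.

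**Illustration for systolic pressure.** All inputs are assumptions: baseline mean 120 mmHg, SD 10, 12 or 15, within-subject correlation r = 0.7, upper limit 140 mmHg, and the same rise in every participant. Follow-up = 120 + rise + 0.7 × (baseline − 120) + residual, with residual SD = SD × √(1 − 0.7²). Simulation with 400,000 draws gave the percentage of those normal at baseline who move to high:

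| SD | No rise | Rise 5 mmHg | Rise 10 mmHg |
|---|---|---|---|
| 10 | about 1.5% | 5.4% | 14.4% |
| 12 | 3.1% | 8.2% | 17.3% |
| 15 | 5.4% | 11.2% | 19.9% |

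If all 32 immediately treated expansion participants were normal at baseline, a 5 mmHg rise would move 32 × 0.054 = 1.7 to 32 × 0.112 = 3.6 of them. With no rise the figures are 32 × 0.015 = 0.5 to 32 × 0.054 = 1.7. The signal is weakened but not absent.

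**The same data as a mean change.** SD of change = SD × √(2 × (1 − 0.7)) = SD × √0.6. The 95% CI half-width is 1.96 × SD × √0.6 / √n.

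- n = 32: 2.7 mmHg (SD 10) to 4.0 mmHg (SD 15)
- n = 16: 3.8 mmHg (SD 10) to 5.7 mmHg (SD 15)

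A 5 mmHg mean rise exceeds the half-width at n = 32 for every assumed SD. At n = 16 it does so only for the smaller SDs (half-width 4.6 at SD 12).

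**Weight.** A 5% gain in an assumed 70 kg adult is 0.05 × 70 = 3.5 kg. The SAP text does not allow it to be placed in any category. In a child assumed to grow 2 to 3 kg a year, growth over nine weeks is 2 × 9/52 = 0.35 kg to 3 × 9/52 = 0.52 kg, so growth distorts the steroid window only slightly.

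**The case against.** The strongest reply is that these harms have another route into the report. Clinically significant abnormalities are recorded as adverse events. SAP 6.1 counts events within 6 months of administration as treatment emergent, which covers the 8 weeks of oral steroid, and tabulates them by age group, treatment group, severity and preferred term. This stands, and it rules out the stronger reading that weight gain and raised blood pressure are hidden or unmeasurable. It does not close the gap for smaller changes. It relies on judgement at sites that SAP 1.4 says were not masked, and the relationship tables cover the ATIMP and the surgery, with no steroid category.

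Second, SAP 6.3 does not say that the shift categories are a normal range. They could be percent weight change or blood pressure grades. SAP 1 places mock-ups and programming instructions in the Data Presentation Specifications, which were not available. A reader might infer that age-appropriate categories do not exist. The documents support only that the SAP text does not state them.

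Third, the illustration depends on its limit. A rise from 110 to 135 mmHg gives no shift with a limit of 140 but does with a limit of 130, and the documents set neither.

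Fourth, height is not a named steroid effect, and weight is covered by the general monitoring statement, not by the itemised schedule. The number of children is uncertain: SAP 1.4 says 3 in the confirmation phase and SAP 1.2 describes the expansion phase as adult, whereas Protocol 4.3.2 allows up to 5 and Protocol 4.3.2.2.5 allows children in the expansion phase. These points stand and narrow the fix.

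**Conclusion.** The point holds in limited form. The SAP plans no post-baseline summary that shows the size of a change in weight or blood pressure, and it applies a normal-range count to weight and height, for which its text supplies no range. Increases that cross no limit and are not judged clinically significant would appear in no planned table; larger ones would still be seen.

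The importance is minor. None of the five primary safety events concerns weight or blood pressure, the steroid is a non-investigational product, and no efficacy or dose-escalation conclusion changes. The figures in the illustration rest wholly on assumed values. That weight and height lack a natural normal range, and that blood pressure norms in children vary with age, is general knowledge and not stated in the documents. The Data Presentation Specifications may supply categories, but the SAP would still plan no change-from-baseline summary. The SAP also cites protocol v12.0, while the amendment history supplied ends at v11.0.

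**What to change.** In SAP 6.3:

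- Add observed value and change from baseline (N, mean, SD, median, range; also percent change for weight) for weight and for systolic and diastolic blood pressure. Present them by visit, treatment group and age group, for the scheduled visits through Week 9. SAP 2.5 and 2.6 already define Study Day 1 and baseline, including for deferred participants after treatment.
- Drop the normal-range shift table and out-of-range count for weight and height.
- Where shift tables are kept, use age-appropriate reference categories for children, stated in the SAP or cross-referenced to the Data Presentation Specifications.
- Treat age-standardised weight in children as optional, given how few children there may be and how short the steroid window is.

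The cost is one extra safety table and a few lines of SAP text. No new data are needed, and no clinical procedure changes.
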